eligibility and baseline status. All screening/baseline safety evaluation results must be available prior to dosing. Patients who enter screening/baseline but are determined not to be eligible to enter the treatment run-in period will be considered as screen failures. See protocol [Section 8.1](#) for permitted re-screening criteria.

Treatment run-in period

Patients who qualify for study eligibility will then enter a single-blind treatment run-in period, during which all patients will receive oral (p.o.) placebo b.i.d. for 2 weeks followed by 50 mg p.o. b.i.d. of active LCZ696 for 2 weeks. Patients who are unable to tolerate either placebo or the 50 mg p.o. b.i.d. dose level, (i.e. do not meet safety criteria as specified in [Table 3-1](#)), will be considered treatment run-in failures and will not be randomized into the double-blind, placebo-controlled study, nor included in the efficacy analysis. At the end of the 4-week treatment run-in period, patients who meet the safety criteria ([Table 3-1](#)) will be eligible for randomization.

Randomized treatment period

At randomization (week 4 visit), eligible patients will be randomized into the study to receive oral (p.o.) doses of LCZ696 or placebo in a 1:1 ratio in a double-blind, placebo-controlled treatment period. All randomized patients will be titrated up to the 100 mg p.o. b.i.d. dose.

All patients will return to the study center approximately 14 days later for assessment of tolerability of the 100 mg p.o. b.i.d. dose (i.e. must meet safety criteria as specified in [Table 3-1](#)). Patients whose assessments demonstrate that they tolerate the 100 mg p.o. b.i.d. dose will be up-titrated to 200 mg p.o. b.i.d. dose, whereas those who do not meet the safety criteria ([Table 3-1](#)) will be titrated back down to the 50 mg b.i.d. dose. Tolerance to the current dose (50 mg b.i.d. or 200 mg b.i.d.) will be again assessed ~14 days later, and those patients who demonstrate tolerance will remain on this dose throughout the remaining treatment period, unless a change in tolerance is noted as defined by the criteria in [Section 16.3 - Section 16.5](#). Those patients who do not tolerate the 200 mg p.o. b.i.d. dose will be titrated down to 100 mg p.o. b.i.d. as outlined in [Section 6.5](#).

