1.3.2 Secondary objective(s)

Secondary objective(s)	Endpoints related to secondary objectives

To evaluate the safety and tolerability of LCZ696 in patients with non-obstructive HCM.	
Adverse events (AEs), vital signs, ECGs, physical examinations and safety labs.

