planning/modifying another study) to relevant Novartis teams for information, consulting, and/or decision purposes. If early efficacy is demonstrated, enrollment of the study may be stopped. No other changes to the design of the study are anticipated as a result of the analysis.

Additional interim analyses may be conducted to support decision making concerning the current clinical study, the sponsor's clinical development projects in general, or in case of any safety concerns.

4 Statistical methods: Analysis sets

For all analysis sets, patients will be analyzed according to the study treatment(s) received.

Throughout this document, 'treatment' refers to one of the two randomized treatment arms assigned to each patient at the Day 29/Week 4 visit, i.e., LCZ696 or Placebo. For the safety analyses that will be presented separately for the treatment run-in period, 'treatment' refers to the corresponding treatments given during the treatment run-in period, i.e. placebo b.i.d. for 2 weeks followed by 50 mg p.o. b.i.d. of active LCZ696 for 2 weeks.

Unless specified otherwise, baseline will be defined as the last non-missing assessment prior to the first dose of study drug administered at the Day 1 visit.

The **safety analysis set** will include all patients that received any study drug.

The **randomized analysis set (RAS)** will consist of all randomized patients.

The **per-protocol analysis set (PPS)** will be a subset of the RAS that will consist of all randomized patients who have no major protocol deviations with relevant impact on PD/efficacy data and who are at least 80% compliant with the overall study drug administration.

The definition for the overall compliance to the study drug administration is provided in [Section 7.2](#).

The analysis sets and protocol deviation codes are related as follows:

Table 4-1 Protocol deviation codes and analysis sets

Category Deviation code	Text description of deviation	Data exclusion
	Patients are excluded from safety analysis in case of these PDs:	Exclude patient from safety analysis set
	Patients are excluded from RAS analysis in case of these PDs:	Exclude patient from randomized analysis set
	Patients are excluded from PD/efficacy analysis in case of these PDs:	Exclude patient from per-protocol analysis set

Category Deviation code	Text description of deviation	Data exclusion

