All laboratory data will be listed by treatment, patient, and visit/time and if normal ranges are available abnormalities will be flagged. A separate listing will be provided presenting all parameters in a patient with any abnormal values. Summary statistics will be provided by treatment and visit/time and will include sample size, mean (arithmetic), SD, median, minimum and maximum. Shift tables using the low/normal/high classification will be used to compare baseline to the worst on-treatment value.

Adverse events

All information obtained on adverse events will be listed by treatment and patient. If any death occurs, then all deaths will be listed by treatment and patient

The treatment emergent AEs are defined as follows for this study:

- For the **treatment run-in period**: Treatment emergent AEs will be the events that started at or after the first dose of study medication and before the start of the double-blind treatment period or events present prior to first dose of study medication but increased in severity during the treatment run-in period based on preferred term.
- For the **randomized treatment period**: Treatment emergent AEs will be the events that started at or after the start of the double-blind treatment period or events present prior to the start of double-blind treatment period but increased in severity based on preferred term.

The number and percentage of patients with treatment emergent AEs will be summarized in the following ways:

- by treatment, primary system organ class (SOC), and preferred term (PT).
- by treatment, primary system organ class (SOC), preferred term (PT), and maximum severity.
- by treatment, Standardized MedDRA Query (SMQ), and preferred term (PT).

Separate summaries will be provided for study related adverse events, serious adverse events and adverse events leading to drug discontinuation.

A patient with multiple adverse events within a primary system organ class (SOC) is only counted once towards the total of the primary system organ class (SOC).

ClinicalTrials.gov and EudraCT

For the legal requirements of ClinicalTrials.gov and EudraCT, two required tables on <on-treatment/treatment emergent> adverse events which are not serious adverse events with an incidence greater than 5% and on <on-treatment/treatment emergent> serious adverse events

and SAE suspected to be related to study treatment will be provided by system organ class and preferred term on the safety set population.

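### The SAP judges run-in AEs from one reference point, the first placebo dose, so an event that starts on placebo and worsens on LCZ696 50 mg is never treatment-emergent on LCZ696

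*SAP*

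**What the plan says.** Protocol Section 3 (treatment run-in period) fixes the order of treatment: "all patients will receive oral (p.o.) placebo b.i.d. for 2 weeks followed by 50 mg p.o. b.i.d. of active LCZ696 for 2 weeks". Patients who cannot tolerate either step "will be considered treatment run-in failures and will not be randomized into the double-blind, placebo-controlled study, nor included in the efficacy analysis".

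SAP Section 7.2 (Adverse events) gives the run-in one TEAE definition with two limbs:

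- **New onset:** "events that started at or after the first dose of study medication and before the start of the double-blind treatment period".
- **Worsening:** "events present prior to first dose of study medication but increased in severity during the treatment run-in period based on preferred term".

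Both limbs refer to the first dose of study medication, which is placebo on Day 1. For the randomized period the same section has a separate definition, whose worsening limb refers to the start of double-blind treatment.

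On layout, SAP Section 4 says that in run-in safety analyses the word treatment "refers to the corresponding treatments given during the treatment run-in period", and names these as "placebo b.i.d. for 2 weeks followed by 50 mg p.o. b.i.d. of active LCZ696 for 2 weeks". SAP Section 7.2 summarises TEAEs by treatment, including a table by maximum severity. Protocol Section 12.5.1 requires the run-in and double-blind periods to be shown separately and all outputs to be by treatment. Its own TEAE definition sets no reference point at the switch from placebo to LCZ696 either.

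The only secondary objective is: "To evaluate the safety and tolerability of LCZ696 in patients with non-obstructive HCM" (SAP Section 1.3.2).

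**The concern.** The run-in is one period that contains two treatments, but the TEAE rule treats it as if it had one. A definition of treatment-emergent normally asks whether the event is new or worse since the treatment in question began. For LCZ696 50 mg, that moment is the Week 2 visit (Day 15 in Protocol Table 8-1), and the SAP sets no reference point there.

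Suppose mild dizziness starts on placebo and becomes severe after the switch. A safety reader would want to see it under LCZ696. The written rule recognises it only by its onset, which was on placebo.

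This matters because of the design. Patients who do not tolerate 50 mg are not randomized, so the double-blind safety comparison is made among patients who have already tolerated the drug. The second half of the run-in is the only LCZ696 exposure before that selection. It is also the larger group: about 44 randomized patients will have taken LCZ696 in the run-in, plus any run-in failures who reached it, against about 22 (44 ÷ 2) assigned to it afterwards.

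**Working it through.** The plan states no figure on this point, so there is none to reproduce. The check is to take each possible course of an event through the SAP text.

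| Course of the event | Limb that makes it a TEAE | Where it is counted |
|---|---|---|
| 1. Starts on LCZ696 50 mg | New onset | LCZ696, if treatment means the one being taken. No error. |
| 2. Starts on placebo, does not worsen | New onset | Placebo. No error. |
| 3. Starts on placebo, worsens on LCZ696 | New onset only; the worsening limb cannot apply because the event was not present before the first dose | Placebo by onset. Nothing makes it emergent on LCZ696. |
| 4. Present before Day 1, worsens in the run-in | Worsening | Not stated. Assignment by date of worsening would be compatible with the text, but is not written. |

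The gap is therefore confined to courses 3 and 4. In course 3, the maximum-severity table has to place an event that was mild on placebo and severe on LCZ696, and the SAP does not say where. By onset, the severe grade appears under placebo.

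**Illustration with assumed counts.** The documents give no event rate. Take 44 patients as the denominator (the number planned for randomization, all of whom will have taken both run-in treatments). For one AE term, assume 4 patients with onset on LCZ696, 4 other patients with onset on placebo and no worsening, and k further patients with course 3.

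- Placebo rate under either rule = (4 + k)/44
- LCZ696 rate, counted by onset = 4/44
- LCZ696 rate, worsening also counted = (4 + k)/44

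| k | Placebo, either rule | LCZ696, by onset | LCZ696, worsening counted |
|---|---|---|---|
| 0 | 9.1% | 9.1% | 9.1% |
| 1 | 11.4% | 9.1% | 11.4% |
| 2 | 13.6% | 9.1% | 13.6% |
| 4 | 18.2% | 9.1% | 18.2% |

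The shortfall in the LCZ696 column is k/44, or 1/44 = 2.3 percentage points per affected patient. The placebo rate is the same under both rules: an event that began on placebo is a placebo event either way. Only the maximum severity shown for placebo can be wrong.

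**The case against.** **Separate columns are already implied.** SAP Section 4 ties run-in treatment to the treatments given, and both documents tabulate by treatment. Two columns are the natural reading, and events that begin on LCZ696 are then handled. This stands. A reader might infer that the SAP credits LCZ696 events to placebo in general, or that it pools the two phases. It says neither, although the Section 4 wording could also be read as one combined sequence. What remains is that columns do not say where an event goes when it spans the switch.

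**Each definition is anchored at the start of its own period, so the SAP is consistent.** True as to structure. But the randomized period has one treatment per patient and the run-in has two, so the same structure gives a wrong count only in the run-in.

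**Placebo events are not inflated.** This stands for incidence, as the working shows. Only severity can be misplaced.

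**The run-in patients are not unselected.** Also right: they have met the eligibility criteria and completed the placebo phase. The accurate statement is that they have not yet been selected on tolerating LCZ696.

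**Intolerance shows up elsewhere.** The safety set includes everyone who took any study drug. AE listings, vital-sign and laboratory summaries and a summary of AEs leading to discontinuation are all planned. These outputs limit the harm, but they do not correct the TEAE count.

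**The rule may be in a document not seen here.** SAP Section 1.1 places derived-variable rules in the programming specification and layouts in the table shells. The Site Operations Manual might also require a new AE record when severity changes, which would lessen course 3. This is possible and cannot be checked. It would not fully cover the registry tables, where SAP Section 7.2 merges consecutive records with the same system organ class and preferred term that are at most 1 day apart, with no break at the switch.

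**Conclusion.** The point holds in a limited form. Under the written SAP rule, an event that starts on placebo and worsens on LCZ696 50 mg is not treatment-emergent on LCZ696, and its maximum severity may be shown under placebo. An event present before Day 1 that worsens in the run-in has no stated treatment. Both can understate LCZ696 events in the only exposure before selection on LCZ696 tolerability.

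The size is unknown. It depends on how many patients follow courses 3 and 4, and the documents give no basis for an estimate; the illustration above shows the mechanism only. The conclusion assumes that no rule in the unseen programming specification or Site Operations Manual closes the gap.

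The primary analysis and the TEAE rule for the double-blind period are untouched. The effect is on descriptive run-in safety tables, but these bear on the sole secondary objective and the repair is cheap, so it should be made. The documents do not support a reading that LCZ696 events are systematically moved to placebo, or that the two run-in treatments cannot be told apart.

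**What to change.** In SAP Section 7.2, replace the single run-in TEAE definition with two windows:

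- **(a) Placebo:** from the first placebo dose to just before the first LCZ696 50 mg dose.
- **(b) LCZ696 50 mg:** from the first LCZ696 50 mg dose to just before the start of double-blind treatment.

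In each window, count events that are new and events whose severity rose above the level just before that window opened. Assign each by its date of onset or worsening. State that run-in AE tables have two columns, placebo and LCZ696 50 mg, each with its own number exposed. An event that starts on placebo and worsens on LCZ696 then appears in both columns, at the severity reached in each.

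The cost is minor SAP wording and programming, with no added patient burden. It relies on the date of worsening being recorded. Protocol Section 10.1.1 requires start and end dates, a severity grade and assessment of severity changes at each visit, but does not show that the date of a change is captured. If it is not, severity at the Week 2 visit, assessed before the new supply is dispensed, could serve as the reference level, provided it is held by visit.

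Optional: tabulate run-in failures on LCZ696 50 mg by the Protocol Table 3-1 criterion that was not met. A failed limit need not be an AE, so this would complement the AE tables, but the repair above does not depend on it.

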7.3 Graphical presentation

A boxplot of the raw vital signs data (sitting pulse rate, sitting systolic blood pressure and sitting diastolic blood pressure) and an arithmetic mean (SE) plot of changes from baseline in vital signs data (sitting pulse rate, sitting systolic blood pressure and sitting diastolic blood pressure) to visualize trends in longitudinal safety data will be created by treatment and over time. Baseline will also be presented as 0 in the arithmetic mean (SE) plot for better visualization of the changes from baseline over time.

In addition, spaghetti plots of vital signs of interest (i.e., sitting systolic blood pressure and sitting diastolic blood pressure) and biochemistry lab parameters of interest (i.e., creatinine, eGFR, potassium and urea nitrogen) will be created by treatment. Note: Only the patients with at least one unscheduled assessment related to AE will be included in the spaghetti plots and all the measurements (scheduled, repeated & unscheduled) of these patients will be presented.

10 Reference list

1. Clinical Trial Protocol, CLCZ696I12201, Protocol Version 02, dated 08 Apr 2022.
2. Site Operations Manual for Protocol No. CLCZ696I12201, Version 06, dated 26 Jan 2022.
